Study Protocol

**Digital Dyadic Empowerment Program on Lifestyle
Modification for Chronic Kidney Disease Management**

Official Title for Year 4 Study:

**Digital Dyadic Empowerment Program (DDEP) on Lifestyle Modification
for Chronic Kidney Disease Management: A Randomized Controlled Trial**

ID: NHRI-EX114-11106PI

NCT06756113

Responsible Party:

Principal Investigator: [name] [[name]]

**Official Title: Professor, Department of Nursing,
College of Medicine**

Affiliation: National Cheng Kung University

Collaborators:

National Health Research Institutes, Taiwan

Document Date: December 13th, 2024

Digital Dyadic Empowerment Program (DDEP) on Lifestyle Modification for Chronic Kidney Disease Management: A Randomized Controlled Trial

Objective

The purpose of this randomized controlled trial is to examine the synergistic long-term effects of the Digital Dyadic Empowerment Program (DDEP) compared to routine care among patients with chronic kidney disease (CKD). Specifically, the study aims to evaluate the program's impact on patients' kidney function, health-promoting lifestyle behaviors, and the dyads' relationship quality over time.

Design

A randomized controlled trial (RCT) will be conducted to test the effect of the Digital Dyadic Empowerment Program (DDEP) compared to routine care, with a single follow-up assessment at 6 months post-baseline. This RCT will adhere to the Consolidated Standards of Reporting Trials (CONSORT) 2010 statement ([Moher et al., 2010](#)) and the CONSORT-EHEALTH guidelines for digital health intervention evaluation ([Eysenbach & CONSORT-EHEALTH Group, 2011](#)) to ensure rigorous reporting and transparency in the study design and outcomes.

Participants

Patients aged over 20 years and diagnosed with CKD at stage 1 to 5 for at least six months will be recruited with the following inclusion criteria: (1) patients can identify a helpful significant other, and both parties are willing to participate; (2) patients are able to communicate in Mandarin or Taiwanese. Patients will be excluded if (1) the significant other is a health care provider, (2) either the patient or significant other has a known mental illness diagnosis, (3) the patient is currently receiving renal replacement therapies, or (4) neither the patient nor the significant other uses a smartphone or the LINE messaging app. Patients who

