do not meet the smartphone or LINE app requirement will be excluded, as they would be unable to receive the intervention in the experimental group, ensuring rigorous randomization.

Setting

Subject will be recruited from outpatient clinics from a medical center in Southern Taiwan.

Sample Size

The estimated number of dyads will be based on the results of the Year 3 feasibility study, as a reference for calculating the effect and the rate of sample lost to follow-up. In the feasibility study, 60 dyads were recruited, and 55 completed the 3-month follow-up, resulting in a retention rate of 91.67%, which exceeds the 12-month retention rate of 64% reported by [Teng and colleagues \(2013\)](#) in a lifestyle modification program. For the formal RCT, the follow-up period has been shortened to 6 months. Efforts will be made to minimize attrition, targeting a dropout rate below 10%. Power analysis calculations, using G*Power software, indicate that for an effect size of 0.25 and a power of 0.8, a sample size of 76 dyads would be required. Adjusting for a 10% dropout rate, 84 dyads would be needed. To further safeguard against potential attrition and maintain robust subgroup analyses, the target recruitment will be 104 dyads. Considering the recruitment efficiency demonstrated in the feasibility study, the plan to recruit 104 dyads remains feasible and appropriate to ensure sufficient power for detecting intervention effects.

Measurements

Data collection will consist of the following instruments: Demographics (e.g., age, gender, education level) and Disease Related Characteristics (e.g., estimated glomerular filtration rate [eGFR], CKD stage), TTM staging Inventory, Dyadic Adjustment Scale-7 (DAS-7), and Health Promoting Lifestyle Profile-II Chinese version revised (HPLP-IIICR).

Procedure

Patients who meet the inclusion criteria will be referred to the study by nephrology outpatient clinic physicians at the study site. Patients attending their routine clinic visit to the nephrology clinic will be identified as potential subject if they meet the inclusion criteria. Dyads will be randomly assigned to either the experimental group or the control group using a pre-generated randomization list prepared via R programming's sample function and by a research assistant.

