After assignment, the dyads will proceed to baseline assessment, which will include collecting demographic information, TTM stage of change, and other selected measures such as DAS-7 and HPLP-IICR. The dyads will complete the instruments in a private room, requiring approximately 15 minutes. Dyads assigned to the intervention group will receive the DDEP revised based on findings from year 3. This intervention will include the installation and usage of a digital platform to facilitate health-promoting behaviors and monitor outcomes. Control group participants will receive routine care without access to the DDEP platform during the study period but may join the platform after the study concludes.

Outcome measures will be evaluated at baseline (T0) and six months post-baseline (T1). Participants will be compensated with a small gift after completing each data collection session.

Data Analysis

Descriptive statistics will be conducted to summarize demographic and clinical characteristics. For ordinal outcome variables, such as CKD stage and TTM stage of change, Fisher's exact test will be used to examine the association between group assignment and pre-to-post change categories (e.g., reverse, maintain, or progress for CKD; advance, maintain, or regress for TTM).

Generalized Linear Mixed Models (GLMM) will be used to analyze differences between groups on continuous outcome indicators, considering the repeated-measures design of the study (Sharpe & Cribbie, 2023). The fixed effects in the models will include measurement time point (baseline and 6 months) and the interaction of group assignment (experimental vs. control) with time point, while random effects will include intercepts and time points to account for individual variability. Missing data will not be imputed. Analyses will be performed using IBM SPSS Statistics software (version 25.0). Statistical significance will be determined using a two-tailed p -value of < 0.05 .

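### The mixed model for continuous outcomes leaves the time coding and treatment contrast unstated, and its random effects are not identified from two occasions in their usual forms

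*Combined protocol and SAP*

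**What the plan says.** The Data Analysis section uses generalized linear mixed models "to analyze differences between groups on continuous outcome indicators". The fixed part reads: "The fixed effects in the models will include measurement time point (baseline and 6 months) and the interaction of group assignment (experimental vs. control", crossed with time. The random part reads: "random effects will include intercepts and time points to account for individual variability". The section does not mention a group main effect, a T0 covariate, a coding for time, a covariance structure, or the coefficient that carries the treatment effect.

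The Design section describes a trial "with a single follow-up assessment at 6 months post-baseline", so each continuous outcome has two occasions. The Procedure section sets the order of events: "After assignment, the dyads will proceed to baseline assessment". The Sample Size section gives its requirement "for an effect size of 0.25 and a power of 0.8", without naming the effect-size metric, the test or a T0-T1 correlation. It adds that "the target recruitment will be 104 dyads".

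**The concern.** With two occasions, a model containing time and group by time can test three different things, depending on whether time is a factor or a 0/1 covariate and whether a group term is also present. Two of them make less use of the T0 data than adjustment for T0 would, so power already paid for may be lost. Separately, two measurements per person give three second moments (two variances and one covariance). A random intercept, a random time effect and a residual can ask for more than those three can supply. If the fit then fails, someone must choose a replacement model after seeing the data. With the contrast also open, the main comparison would not be fully prespecified.

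**Working it through.** **Inputs.** From the documents: two-sided 5%, two occasions, effect size 0.25, power 0.8, 76 dyads before dropout, 84 after, target 104, dropout 10%. Assumed: 1:1 allocation, SD of 1 at both times, T0-T1 correlation rho, complete pairs. Analysed: 104 x 0.9 = 93.6, taken as 94, or n = 47 per arm.

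**The plan's own figure.** 76 x 1.10 = 83.6 gives the 84. The 76 did not reproduce from the stated inputs. With 0.25 taken as f, two-occasion calculations give 34 (interaction, rho 0.5), 66 (rho 0), 98 (between factors, rho 0.5) or 128 (one-way or ANCOVA). This does not show 76 to be wrong, because inputs are missing. It does mean that the sample size cannot show which contrast was intended. Nothing below depends on it.

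**Fixed effects.** The rank of the design matrix shows what group by time tests.
- Time as a factor, no group term: rank 4 against 2 for time alone. Group by time has 2 df and tests the T0 and T1 differences jointly.
- Group term included: rank 4 against 3. Group by time is the 1-df difference in change.
- Time as a 0/1 covariate, no group term: rank 3 against 2. Group by time is the 1-df T1 difference with T0 means held equal, which has the same large-sample variance as ANCOVA.

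**Efficiency.** For a T1 difference d with no true T0 difference:
- Change contrast: variance 4(1 - rho)/n.
- T0-adjusted contrast: variance 2(1 - rho^2)/n.
- Ratio, adjusted over change: (1 + rho)/2.
- 2-df test: noncentrality d^2 / [2(1 - rho^2)/n], the same as the adjusted test but spread over 2 df.

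At rho 0.5 and d = 0.5:
- Change: SE = sqrt(2/47) = 0.206, so d/SE = 2.42.
- Adjusted: SE = sqrt(1.5/47) = 0.179, so d/SE = 2.80.
- 2-df: noncentrality = 2.80^2 = 7.83.

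Noncentral t and F then give power. The adjusted figures multiply the variance by 1 + 1/(2n - 4) for the estimated T0 slope.

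| d | rho | 2-df | change | T0-adjusted |
|---|---|---|---|---|
| 0.5 SD | 0.4 | 0.640 | 0.591 | 0.740 |
| 0.5 SD | 0.5 | 0.693 | 0.669 | 0.786 |
| 0.5 SD | 0.7 | 0.857 | 0.872 | 0.916 |
| 0.5 SD | 0.8 | 0.954 | 0.967 | 0.978 |
| 0.25 SD | 0.5 | 0.216 | 0.224 | 0.280 |
| 0.25 SD | 0.7 | 0.301 | 0.341 | 0.386 |
| 0.25 SD | 0.8 | 0.411 | 0.475 | 0.511 |

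The metric decides which rows apply. A standardised difference of 0.25 is 0.25 SD. A two-group f of 0.25 is 2 x 0.25 = 0.5 SD. An f of 0.25 for the 2x2 interaction is 4 x 0.25 = 1.0 SD, where all three tests exceed 99%.

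Whatever the effect size, for 80% power the change contrast needs about 2/(1 + rho) times the dyads of the adjusted contrast: 1.33 at rho 0.5, 1.18 at 0.7, 1.11 at 0.8. The 2-df test needs 9.635/7.849 = 1.23 times as many.

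**Type I error.** With no effect, rho 0.5 and n = 47 (400,000 simulated trials), the 2-df, change and adjusted tests reject 5.07%, 5.03% and 5.05%.

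**Random effects.** Write a for the intercept variance, b for the time variance, c for their covariance and e for the residual variance.
- Unstructured, time 0/1: Var(T0) = a + e; Cov = a + c; Var(T1) = a + 2c + b + e. Four unknowns, rank 3: not identified.
- Time as a random factor: Var(T0) = Var(T1) = a + b + e; Cov = a. Three unknowns, rank 2: b and e cannot be separated.
- Uncorrelated slope, time 0/1: Var(T0) = a + e; Cov = a; Var(T1) = a + b + e. Rank 3 of 3, just identified, with b = Var(T1) - Var(T0). If the two variances are equal, b is estimated at zero in about half of trials (20,000 simulated). With time coded -0.5/0.5 the rank drops to 2.
- Unstructured 2x2 residual, no random effects: three parameters, rank 3, always identified.

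**The case against.** The strongest reply is that a group-by-time interaction is a conventional and valid way to compare groups before and after treatment. The plan classifies its ordinal outcomes by change, so a difference in change may be what is meant. Preferring baseline adjustment is then a choice between valid analyses. The fixed effects as listed also contain no group term, which fits the efficient 0/1 coding. All of this stands. A reader might infer that the plan is committed to an inefficient test, or that its type I error is wrong. The documents support neither: the coding is simply not stated, and all three tests hold 5%.

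The size of the loss also rests on assumptions. For eGFR across CKD stages 1 to 5, a correlation above 0.7 over six months is plausible. At rho 0.8 and 0.5 SD the change contrast loses only about one point.

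The ranking further requires that T0 is unaffected by knowledge of the allocation, and the protocol places baseline after assignment. At rho 0.5, suppose knowing the allocation shifts scores by 0.1, 0.2 or 0.3 SD at both times. The adjusted contrast then rejects 6, 8.5 or 13% under no effect, and the change contrast stays at 5%. If the shift is at T0 only, the adjusted contrast rejects 6, 8.5 or 13% and the change contrast 8, 16 or 30%. Neither contrast is safe in both cases, which is why the order of the visit matters.

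On the random effects, a reader might infer a biased treatment estimate. Non-identification of the variance components need not bias the contrast or change its standard error. Finally, because DAS-7 concerns both members, a reader might infer that two scores per dyad would be analysed as independent. No section proposes that, so it forms no part of this point.

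**Conclusion.** The point holds as a gap in specification with an inexpensive improvement, and it should be fixed. That the coding, contrast and covariance structure are unstated is certain from the text. So is the non-identification of the unstructured and factor forms from two occasions. Its practical consequence is limited to possible non-convergence and an unplanned replacement model.

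The loss of power is conditional. It arises only under the factor or group-term reading. At 47 per arm and 0.5 SD, the shortfall against the T0-adjusted contrast is about 9 points (2-df) and 12 points (change) at rho 0.5, 6 and 4 points at rho 0.7, and 2 and 1 points at rho 0.8. It vanishes if 0.25 is f for the 2x2 interaction. Correlation, effect metric and 1:1 allocation are assumptions, and the ranking presumes that T0 is not influenced by known allocation.

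**What to change.** For each continuous outcome, name one 1-df treatment contrast: the group difference at T1 adjusted for T0. Fit it as ANCOVA, or as a two-occasion model with time, a single group-at-T1 term, an unstructured 2x2 residual covariance and no random time effect. The two-occasion model also keeps dyads with T0 only, which is consistent with the plan not to impute. If the sponsor already means 0/1 time with no group term, say so and drop the random time effect.

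Collect T0 before the allocation is revealed, at the same visit. If that cannot be done, report the change contrast as a sensitivity analysis and state the assumption about T0.

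The cost is revised analysis wording, SPSS syntax and a small reordering of the baseline visit. No new measurements and no extra dyads are needed.
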